#### **4.5.2 Secondary Efficacy Endpoints**

All analyses of secondary efficacy endpoints as defined in section 2.2.2 will be performed for population A and for population C, using their respective baseline definition (see 4.4.2).

For all secondary endpoints measured on a continuous scale, the same MMRM model used for the change from baseline BCVA will be employed. Nominal p-values for treatment effect will be reported for all post-baseline visits without correction for multiple testing.

Binary endpoints will be analyzed using Generalized Estimating Equations (GEE) with a binomial distribution, logit link function for odds ratios and identity link for risk differences, and unstructured covariance. In case of convergence issues, other covariance structures, such as AR(1) covariance structure, will be used.

The model will include the categorical covariates of treatment group, visit, and visit by treatment group interaction and randomization stratification indicator for presence of RAP or PCV and the continuous covariate of baseline outcome measure.

Least squares means on the probability scale for each treatment arm with the corresponding 95% confidence intervals and odds ratios relative to the control arm will be computed for all post-baseline visits.

Data transformation (e.g., logarithmic transformation) may be applied as appropriate. Other statistical models and additional analyses may also be performed as appropriate. Fisher's exact test may be used for binary endpoints in case GEE models do not converge.

In addition, the influence of baseline parameters will be evaluated as covariates in the MMRM model and in subgroup analysis as appropriate (see Section 4.5.5 ).

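### SAP 4.5.2's identity-link GEE will rarely or never give a valid risk difference for 20/40 or better and 20/200 or worse, and its named fallbacks supply no adjusted one

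*SAP*

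**What the plan says.** SAP 4.5.2 covers four binary secondary endpoints, listed in SAP 2.2.2: a gain of 15 or more letters, 20/40 or better, 20/200 or worse, and dry retina by SD-OCT. Each is analysed in Populations A and C.

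- **Model.** "Binary endpoints will be analyzed using Generalized Estimating Equations (GEE) with a binomial distribution", with "logit link function for odds ratios and identity link for risk differences, and unstructured covariance". The terms are arm, visit, their interaction, and "randomization stratification indicator for presence of RAP or PCV and the continuous covariate of baseline outcome measure".
- **Output.** "Least squares means on the probability scale for each treatment arm with the corresponding 95% confidence intervals", and odds ratios against control, "will be computed for all post-baseline visits". The SAP does not say which of the two link models supplies the LS means.
- **If the fit fails.** "In case of convergence issues, other covariance structures, such as AR(1) covariance structure, will be used". In addition, Fisher's "exact test may be used for binary endpoints in case GEE models do not converge". The section also permits other, unnamed models where appropriate.

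Protocol 6.6.2 promises each group's proportion with a 95% interval, the difference in response rate, the odds ratio and Fisher's exact test, all without adjustment.

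**The concern.** An identity link does not keep fitted probabilities between 0 and 1. Once a fitted value leaves that range the binomial variance p(1 − p) is no longer positive, and the estimating equations have no valid solution there. The risk is greatest when the outcome depends steeply on a continuous covariate with a wide range. That describes final acuity category against entry BCVA.

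Changing the working covariance leaves the link as it was. Fisher's exact test gives a p-value and no adjusted risk difference. If the model fails, what remains is the unadjusted difference of protocol 6.6.2, or a replacement model chosen after the failure.

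The second issue is the displayed proportions. A logit-model LS mean is the probability at average covariate values. Because the logit is curved, this is not the average probability over the arm's patients, so the tabulated proportions, and differences read from them, can disagree with the response rates.

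**Working it through.** **1. The plan's own design figure.** The SAP gives no rate or power for any binary endpoint; the nearest figure is the Population A power statement (SAP 2.3.1). With 10% dropout, n = 0.9 × 68 = 61.2 and 0.9 × 45 = 40.5. SE = 13.5 × √(1/61.2 + 1/40.5) = 2.73. Minimum detectable difference = 1.2816 × 2.73 = 3.50 letters. Power = Φ(5.9/2.73 − 1.2816) = 0.81. Both figures reproduce.

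**2. Why a straight line fails.** From the documents: entry BCVA 24 to 73, 20/40 starting at 69 letters (protocol 4.2.1), SD of change 13.5. Assumed: mean gain 8 letters regardless of baseline, normal errors, and 20/200 or worse taken as 38 letters or fewer (5 letters per line).

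- *20/40 or better:* P(b) = Φ((b + 8 − 69)/13.5). This gives P(73) = 0.81, P(56) = 0.36, P(24) = 0.003. The line through 56 and 73 letters has slope (0.813 − 0.356)/17 = 0.0269 per letter. It reaches zero at 56 − 0.356/0.0269 ≈ 43 letters and would be about −0.51 at 24 letters. With a mean gain of 10 the corresponding values are 40 letters and −0.41.
- *20/200 or worse:* P(b) = Φ((38 − b − 8)/13.5). This gives P(24) = 0.67, P(40) = 0.23, P(73) = 0.001. The line through 24 and 40 letters reaches zero at about 48 letters (47 with a mean gain of 10).
- *Gain of 15 or more:* with gain unrelated to baseline, P = Φ((8 − 15)/13.5) = 0.30 at every baseline, so this argument does not apply.

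A fitted line would compromise between such slopes. In simulation, ordinary least squares for 20/40 or better in Population A still gave fitted values from about −0.40 to 0.87.

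**3. The model as specified.** Simulation at planned size: Population A has 203 patients and 4 arms × 9 visits = 36 cells; Population C has 2 arms × 6 visits = 12 cells. There were 60 datasets in each of four scenarios. Assumed: baseline mean 55 to 62 letters before truncation to 24–73, mean gain 8 to 10, slope of gain on baseline 0 to −0.3, RAP/PCV 25%, dry rate 15 to 35% in Population A and 30% in Population C. A fit counts only if all fitted probabilities lie inside 0 to 1.

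| Endpoint | Valid identity-link fits, Population A | Population C |
|---|---|---|
| 20/40 or better | 0% | 0% |
| 20/200 or worse | 0% | 0% |
| Gain of 15 or more | 0–10% if gain depends on baseline; 55% if not | 0% |
| Dry retina | 65–77% | 7–22% |

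Dry retina fits more often in Population A because eligibility requires fluid at entry, so baseline status is constant and drops out.

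Further checks:

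- *Standard GEE routine, 12 Population A datasets, one scenario:* no valid fit for any BCVA endpoint under independence or unstructured covariance.
- *Separate simulation (baseline about N(56, 12) truncated, gain rising from 4 to 8 letters):* identity fits converged in 0/40 (exchangeable) and 0/60 (independence) for each acuity-threshold endpoint, and in 9/40 and 34/60 for a gain of 15 or more.
- *Week 36 alone:* valid identity fits in 0–16% of datasets for 20/40 or better and 0% for 20/200 or worse. For a gain of 15 or more, a straight-line fit left the range in at most 3%, so that endpoint's failures come from the multi-visit model.

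**4. LS means from a logit fit.** Control arm, Week 36, Population A, LS mean against observed rate: 20/40 or better 0.336 against 0.380; 20/200 or worse 0.017 against 0.055; gain of 15 or more 0.304 against 0.309; dry retina 0.338 against 0.339. In Population C, 20/40 or better was 0.142 against 0.249.

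Under a true 5.9-letter effect, the LS-mean difference in 20/40 or better exceeded the standardised difference by 2.3 to 4.1 points over five sets of assumptions. Another set gave 18.9 − 13.5 = 5.4 points. For a gain of 15 or more the excess was 0.1 to 0.7 points. For 20/200 or worse the LS-mean difference was too small.

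**5. Marginal standardisation.** Averaging the logit predictions over patients recovered the observed control rates: 0.382 against 0.380, 0.054 against 0.055, 0.309 against 0.309, and 0.340 against 0.339 (20/40, 20/200, gain, dry retina).

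**6. Sparse data.** For 20/200 or worse even the logit GEE converged in only 7 of 40 datasets, because of empty arm-by-visit cells.

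**The case against.** A reader might infer that the identity model cannot be fitted for most of the binary endpoints. The documents do not support that. In Population A two of four fail consistently; dry retina often fits, and a gain of 15 or more letters depends on how gain relates to baseline. With no response rates in the documents, every count rests on assumptions and partly on software. The unstructured covariance that the SAP puts first was checked in only 12 datasets of one scenario.

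A reader might also infer that the risk difference will be missing altogether. Protocol 6.6.2 already promises a simple difference in response rate, Fisher's test is a pre-written fallback, and the SAP allows other models. What is at risk is the adjusted risk difference; the open clause names no replacement, so any would be chosen after the failure.

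Nor do LS means always overstate effects. The direction reverses for 20/200 or worse, and the gap is negligible for a gain of 15 or more. The SAP does not claim that LS means equal response rates, and a covariate-specific probability is a legitimate quantity if labelled as such.

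Finally, these are secondary analyses without multiplicity correction in a study that SAP 4.8 calls hypothesis-generating. That limits the consequence; it does not make the rule workable.

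**Conclusion.** The point holds for 20/40 or better and 20/200 or worse: as written, the identity-link model rarely or never has a valid fit (0% in the multi-visit simulations in both populations; 0–16% and 0% at Week 36 alone). It is also unreliable for a gain of 15 or more letters, depending on assumptions, and for dry retina in Population C. Neither named fallback yields an adjusted risk difference.

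If the LS means come from the logit model, they overstate the difference in 20/40 or better by roughly 2 to 5 points under a 5.9-letter effect, understate it for 20/200 or worse, and barely matter for a gain of 15 or more.

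The direction is secure because it follows from the link and the baseline range. The exact percentages are not, because they rest on assumed baseline distributions, gains and response rates. The change should be made before unmasking; the primary BCVA MMRM is unaffected.

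**What to change.** In SAP 4.5.2:

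1. Delete the identity-link model. Keep the logit GEE for odds ratios.
2. Report each arm's response rate and the risk difference against Arm A by marginal standardisation: predict for every patient under each arm, average over the observed covariates, and give delta-method or bootstrap 95% intervals. These replace the probability-scale LS means.
3. Name 20/200 or worse in advance as the sparse endpoint. Do not trigger the switch by any empty arm-by-visit cell: that would let an early visit change the Week 36 method, and it occurred for this endpoint in 32% to 100% of simulated datasets depending on the assumed baseline.
4. For that endpoint report the Week 36 risk difference with Mantel-Haenszel weights, over the randomisation strata in Population A and over RAP/PCV only in Population C. There, 68 letters or fewer at Week 12 with at least one letter gained means 67 or fewer on Day 1, so the 69-or-better stratum is empty by definition.

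Cost: SAP wording and a little programming, no new data. If the logit GEE does not converge for 20/200 or worse, that endpoint will have no odds ratio and no earlier-visit estimates. The Mantel-Haenszel estimate does not itself deal with dropout, so the SAP should state how missing Week 36 values are handled.

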#### **4.5.3 Exploratory Efficacy Endpoints**

Additional exploratory analyses may be performed as warranted in order to more fully understand the relationship over time between parameters and either nominal dose or concentration of RO6867461. They will be described here.

- Proportion of patients with resolution of PCV over time
- Proportion of patients with resolution of RAP over time

#### **4.5.4 Sensitivity Analyses**

Effects of prognostic factors on the BCVA change from baseline will be investigated using the MMRM model described in section 4.5.1. The measurement at BL (baseline) of each of the following variables may be used as covariates in the model:

- Age
- CNV component area, (FFAArea)
- LLD (Difference between BCVATOT for the BCVA assessment and LLVATOT for the LLVA assessment)

The sensitivity analyses will be performed separately for each covariate in populations A and C.

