4.6.4.3 Exploratory Assessments

4.6.4.3.1 Low Luminescence Visual Acuity

On Day 1, BCVA at a starting test distance of 4 meters under low luminescence (LLVA) will be measured prior to dilating eyes by trained and certified VA examiner masked to study treatment assignment.

LLVA is mandatory at the Day 1 visit only. At the discretion of the Investigator and in agreement with the patient, LLVA (optional) can be assessed at the other time-points detailed in the SoA ([Appendix 1](#)). Participation in the optional LLVA assessment will be recorded locally and data entered in the eCRF.

LLVA will be measured by placing a 2.0-log-unit neutral density filter (Kodak Wratten 2.0 Neutral Density Filter) over the best correction for that eye and having the participant read the normally illuminated ETDRS chart (using the set of three Precision Vision™ or Lighthouse distance acuity charts [modified ETDRS Charts 1, 2, and R]). A VA Procedure Manual will be provided to the Investigators. VA examiner and VA examination room certifications will be obtained before any VA examinations are performed.

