6. STATISTICAL CONSIDERATIONS AND ANALYSIS PLAN

6.1 DETERMINATION OF SAMPLE SIZE

6.1.1 Sample Size and Power for Treatment-Naive Population Evaluation

The sample size for the treatment-naive population is based on the primary efficacy outcome of mean change in BCVA from baseline to Week 36. Each RO6867461 dose

or dose regimen group (Arms B, C, and D) will be compared to the control group (Arm A).

Consider 68 patients randomized to Arm A and 45 randomized to each of Arms B, C, and D, with a drop-out rate of 10%. Assuming a standard deviation of 13.5 letters, this sample size would provide approximately 80% power to detect a true difference of 5.9 letters at the one-sided α level of 10%. The minimum detectable difference would be approximately 3.5 letters.

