### **2.3 DETERMINATION OF SAMPLE SIZE**

#### **2.3.1 Sample Size and Power for Treatment-Naive Population Evaluation**

The sample size for the treatment-naive population is based on the primary efficacy outcome of mean change in BCVA from baseline to Week 36. Each RO6867461 dose or dose regimen group (Arms B, C, and D) will be compared to the control group (Arm A).

Consider 68 patients randomized to Arm A and 45 randomized to each of Arms B, C, and D, with a drop-out rate of 10%. Assuming a standard deviation of 13.5 letters, this sample size would provide approximately 80% power to detect a true difference of 5.9 letters at the one-sided  $\alpha$  level of 10%. The minimum detectable difference would be approximately 3.5 letters.

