#### **4.5.1 Primary Efficacy Endpoint**

##### **4.5.1.1 Evaluation in the Treatment-Naïve Population**

For the evaluation of efficacy in the treatment-naïve population, all patients in Population A will be used.

The primary efficacy variable is the BCVA change from baseline to Week 36. The primary efficacy analysis will be performed using a Mixed Model for Repeated Measurement (MMRM) model. The model will include the categorical covariates of randomization stratification indicator for presence of RAP or PCV, treatment group, visit, and visit by treatment group interaction and the continuous covariate of baseline BCVA. An unstructured variance-covariance model will be used to account for within-patient correlation, but another variance-covariance structure, such as AR(1), may be used in case of convergence issues.

In case of a significant departure from the normality assumptions required for the MMRM, a nonparametric Mann-Whitney  $U$  test will be used to compare change from baseline between treatment arms at given visits.

The primary statistical tests will test the null hypotheses:

$H_0$ : no difference between each of the treatment group (Arms B, C, or D) and the control group (Arm A), in mean BCVA change from baseline to Week 36 vs.

$H_A$ : Arms B, C or D means are different from Arm A mean.

The model-based estimate of the difference between each of the treatment group (Arms B, C, and D) and the control group (Arm A) at Week 36, together with 95% confidence intervals and corresponding p-value will be reported as the primary efficacy measures in this population.

The mean and 95% confidence interval (CI) within each treatment group and for the difference in change from baseline between RO6867461 treatment groups (Arms B, C, and D) and the control group (Arm A) at the other time-points will also be reported. There will be no formal correction for multiple comparisons.

For the primary endpoints, a statistically significant difference at week 36 between any of the treatment Arms B, C, or D and Arm A will be concluded if the corresponding unadjusted 2-sided p-value is below 0.2.

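### The primary MMRM omits three baseline variables that the SAP itself lists as prognostic (age, CNV component area, low-luminance deficit), forgoing a possible but unquantified gain in precision

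*SAP*

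**What the plan says.** SAP 4.5.1.1 fixes the primary MMRM for the treatment-naive comparison. Besides the stratification indicator for RAP or PCV it contains "treatment group, visit, and visit by treatment group interaction and the continuous covariate of baseline BCVA". SAP 4.5.1.2 refers back to the same model for Population C, the incomplete responders, whose baseline is Week 12 (SAP 4.4.2).

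SAP 4.5.4 then turns to three further variables: age, CNV component area, and LLD, defined as BCVA minus low-luminance visual acuity (LLVA). It introduces them with "Effects of prognostic factors on the BCVA change from baseline will be investigated using the MMRM model" and closes with "The sensitivity analyses will be performed separately for each covariate in populations A and C". Each variable is therefore tried alone, and no model described in the SAP holds all three.

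All three are scheduled before treatment starts:

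- Age is part of the demographic data (Protocol 4.6.1.1), taken at screening.
- CNV component area comes from the screening fluorescein angiogram, which is also used for eligibility (Protocol 4.2.1 and 4.3.1).
- LLD needs LLVA, on which Protocol 4.6.4.3.1 says "LLVA is mandatory at the Day 1 visit only". At later visits LLVA is optional.

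**The concern.** In a randomised comparison, adjusting for pre-specified baseline variables does not bias the treatment effect. It reduces the standard error to the extent that the variables predict the outcome beyond what is already in the model. The SAP singles out three such variables, and the data are to be collected anyway. Fitting the deciding model without them gives up whatever precision they carry, while one-at-a-time models elsewhere do nothing for the primary contrast.

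A second matter concerns Population C. SAP 4.5.4 takes each covariate at baseline, which for that population can be read as Week 12. LLVA is optional then, and the missing-data section (SAP 4.7) deals with the outcome and gives no rule for missing covariates. A standard MMRM drops patients with a missing covariate, so a Week 12 LLD covariate could remove patients from a population planned at only about 40 completers per arm.

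**Working it through.** **Inputs.** For the treatment-naive comparison, Protocol 6.1.1 and SAP 2.3.1 give 68 patients in Arm A and 45 in each of Arms B, C and D, 10% drop-out and an SD of 13.5 letters. The target is "approximately 80% power to detect a true difference of 5.9 letters", tested "at the one-sided α level of 10" percent. The SAP decision rule, "corresponding unadjusted 2-sided p-value is below 0.2", is the same threshold in the favourable direction. For incomplete responders, SAP 2.3.2 gives 68 per arm, 65% qualifying, 10% drop-out, an SD of 9.7 and a difference of 4.7 letters.

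**Reproducing the plan, Population A.** Completers: 0.9 × 68 = 61.2 and 0.9 × 45 = 40.5.

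- SE = 13.5 × √(1/61.2 + 1/40.5) = 2.735 letters.
- Power = Φ(5.9/2.735 − 1.2816) = 80.9% (80.7% with the noncentral t), against about 80% stated.
- Minimum detectable difference = 1.2816 × 2.735 = 3.50 letters, against 3.5 stated.

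**Reproducing the plan, Population C.** Completers: 68 × 0.65 × 0.9 = 39.78 per arm.

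- SE = 9.7 × √(2/39.78) = 2.175 letters.
- Power = Φ(4.7/2.175 − 1.2816) = 81.0%.
- Minimum detectable difference = 2.79 letters, against 2.7 in the SAP and 2.8 in Protocol 6.1.2. That protocol section also gives the target as 4.8 letters, where power is 82.3%. Either target fits about 80%.

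**Effect of joint adjustment.** Let R² be the share of the variance left after baseline BCVA and the RAP/PCV stratum that the three covariates jointly explain. The documents give no value, so R² is an assumption and a range is shown. Adjusted SE = SE × √(1 − R²), and the equivalent gain in patients is 1/(1 − R²) − 1.

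| Assumed R² | SE, Pop. A | Fall in SE | Power at 5.9 letters, Pop. A | Equivalent extra patients | Power at 4.7 letters, Pop. C |
|---|---|---|---|---|---|
| 0% | 2.735 | 0 | 80.9% | 0 | 81.0% |
| 2% | 2.707 | 1.0% | 81.5% | 2% | 81.6% |
| 5% | 2.665 | 2.5% | 82.4% | 5% | 82.5% |
| 10% | 2.594 | 5.1% | 84.0% | 11% | 84.0% |
| 15% | 2.521 | 7.8% | 85.5% | 18% | 85.6% |

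**Limits of the calculation.** It is a single-visit, completers-only approximation. It takes 13.5 letters (9.7 in Population C) as the residual SD, although the documents do not say whether these are raw or residual. If they are raw, the power of the planned model is already above 81% and there is less to gain. In an MMRM, the reduction at Week 36 is secured only if the covariate effects may differ by visit. A single coefficient shared by all visits need not fit Week 36 well.

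**The case against.** The strongest reply is that nothing is broken. The plan fixes one primary model in advance, already adjusts for continuous baseline BCVA and the RAP/PCV stratum, and meets its own power target. A parsimonious primary model with further covariates examined elsewhere is a legitimate choice in a study described as hypothesis-generating (SAP 4.8). All of this stands, and it sets the size of the point.

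It is also fair to say that the gain may be small or nil. Listing variables whose effects are to be investigated does not document their strength. LLD is partly made of BCVA, so with Day 1 BCVA already in the model, adding LLD is algebraically the same as adding LLVA. That makes it a separate measurement and not a redundant one, but its added value is unknown.

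A reader might infer four stronger things that the documents do not support:

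- **That the primary estimate is biased or the trial underpowered.** Randomisation protects the estimate, and the stated power reproduces.
- **That adjustment would shrink the standard error of every primary contrast.** It does so only if the covariates predict BCVA change beyond what the model already holds.
- **That the covariate models are after the fact or merely optional.** They are named in the SAP. The wording is mixed: it says the covariates may be used, but also that the analyses will be performed.
- **That the plan invites choosing among adjusted results.** SAP 4.5.1.1 states one primary model and attaches the significance rule to the primary endpoint. SAP 4.5.4 is headed as sensitivity analysis.

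**Conclusion.** The point holds as one of efficiency. The SAP lists three variables as prognostic for its primary endpoint, schedules all of them before the first dose, and includes them jointly in no model. If together they explain 5% to 15% of the remaining variance, power at 5.9 letters rises from about 81% to between 82% and 86%, equivalent to 5% to 18% more patients. At 2% the gain is 0.6 percentage points, and at zero there is none.

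These figures rest on an assumed R², on reading 13.5 letters as a residual SD, and on a single-visit approximation to the MMRM. The timing of the covariates in Population C does not depend on R² and needs a stated rule if LLD is to be used there at all.

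**What to change.** Before unmasking, amend SAP 4.5.1.1, 4.5.1.2 and 4.5.4 as follows:

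- **Primary model.** Add age, screening CNV component area and Day 1 LLD together as continuous covariates. Let their effects, and that of baseline BCVA, vary by visit. If that model does not converge, fall back to main effects.
- **Missing covariate values.** Replace each with the mean of that covariate pooled across arms, so that no patient is lost.
- **Population C.** Keep Week 12 BCVA as the baseline covariate and state that the Day 1 or screening values of the other three are used, because LLVA is optional at Week 12. The trade-off is that lesion area then predates the first three injections, although angiography is also scheduled at Week 12.
- **Other models.** Keep the model now written as a sensitivity analysis. Keep the one-at-a-time models as exploratory, since they answer a different question about each factor.

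No new data are needed, only a few sentences in the SAP. BCVA is scheduled at nine post-baseline visits (Weeks 4 to 36 in four-week steps), so visit-specific effects of the three covariates mean 9 × 3 = 27 coefficients in Population A. After Week 12 there are six visits, hence 6 × 3 = 18 in Population C. The charge against the Week 36 contrast itself is about three degrees of freedom. The downside is that small loss, with possibly no gain if the covariates add nothing beyond baseline BCVA.
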